Participants: 70 overweight and obese healthy male and female volunteers aged between 18 and 65 years with body mass index (BMI) of 25-35 kg/m².

Support of number of volunteers: Based on previous work we anticipate that a hypo-caloric diet alone will cause a weight loss of 3.0 ± 2.5 kg, whilst the addition of propionate-ester will cause a weight loss of 5.0 ± 2.5 kg. A power calculation shows that 26 volunteers will be need per group to detect a significant difference between groups ($p=0.05$, 0.80 power). 70 volunteers will be recruited to allow a 25% drop-out rate.

Visit 1: Health Screening

Participants will attend the NIHR/Wellcome Trust Imperial Clinical Research Facility at Hammersmith Hospital where their eligibility will be assessed. They will have a blood test (FBC, ALT, HbA1C, renal function, and lipids) and height and weight measurements will also be taken. They will also have an electrocardiogram (ECG) and blood pressure will be recorded. All women of childbearing age will have a pregnancy test.

Participants will be told not to start any other new diets or intensive exercise regimes during the study period as this may give us conflicting results.

Visit 2: Acclimatization visit (Week 0)

The main objective of this visit is to fully acclimatize the participants to the study before the baseline visit.

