The day prior to the study visit, participants will be requested to refrain from strenuous exercise and alcohol. Participants will then be requested to fast overnight (they are allowed to drink water) and will come to the NIHR/Wellcome Trust Imperial Clinical Research Facility at Hammersmith Hospital the following morning. Fasting saline flushes will be done through an intravenous peripheral cannula at -10 and 0 min. Resting energy expenditure will be measured with a standard indirect calorimeter. The calorimeter captures expired air from a large, transparent canopy, worn over the head and thorax, and is typically very well tolerated. Each participant will be asked to lie in a semi-recumbent position under the canopy. Once the carbon dioxide content of the air entering the chamber has stabilised, measurements will be taken for 20 min in order to assess the participants' resting metabolic rate (RMR) and respiratory quotient (RQ). The calories needed per day for each subject will be estimated and a -500 kcal/day diet will be provided to the participants to follow for the rest study period. Participants will be asked to complete a 7days-food diary in order to form a suitable individualised diet. A weight management booklet will be designed to each participant, where their resting energy requirement will be estimated and a healthy diet plan will be designed. This will also include a supplementary material of the portions required and list of different substitutes to be taken per food group. The same booklet content was previously designed and used in a trial that was ethically approved with a reference number of 12/LO/0139 version 2: 31/07/2012.

Participants will then receive a standardised breakfast (0 min). Postprandial saline flushes will be given at 15, 30, 60, 90, 120, 180, and 240 min.

Appetite and satiety will be assessed by visual analogue scale every 60 min and breath hydrogen concentration will be measured at the same time, as a marker of colonic fermentation. Food intake will be assessed at 240 min by offering a free buffet meal served in excess.

Visit 3: Study visit 1 (Week 1)

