The same measurements collected during the acclimatization visit will be repeated. The only difference would be in collecting 10 ml of postprandial blood, instead of flushing saline, at each time point of 15, 30, 60, 90, 120, 180, and 240 min to measure hormones and metabolites. These will include glucose, insulin, gastrointestinal and appetite hormones (GLP-1, pro-glucagon-derived peptide, PYY, PP, Ghrelin, Cholecystokinin), and short chain fatty acids level

Participants will be randomised to take 10 g of Propionate ester or Inulin (control) dietary supplement once a day for 84 days (12 weeks). Supplements will be given to participants in ready-to-use sachets and instructed to mix the contents into their -500 kcal/day individual diet. An independent researcher (i.e. not linked to the study) will be given the task of randomisation, which will be by sealed envelopes.

Urine will be collected throughout the study visit to measure propionate and urea concentrations. Subjects will empty their bladder before the test breakfast and collect all urine thereafter for a period of 240 min. Subjects will be provided with an appropriate measurement container to collect urine and will be asked to note the total volume following each collection.

Subjects will be asked to collect a stool sample to assess propionate levels. Subjects will collect a sample of the first stool they pass after 10:00 pm on the study day. Participants will be provided with detailed instructions of how to do this and will be given appropriate containers.

Visits 4 and 5: Study visits 2, 3 (Week 4 and week 8):

Will involve short visits to monitor weight and dietary compliance to the diet, through collecting 7-days food intake diary and taking anthropometry measurements.

Visit 6: Study visit 4 (Week 12):

At the end of 84 day supplementation period, participants will attend the NIHR/Wellcome Trust Imperial Clinical Research Facility at Hammersmith Hospital to and all measurements collected during Study Visit 1 will be repeated.

PARTICIPANT ENTRY**INCLUSION CRITERIA**

- Healthy overweight and obese volunteers (body mass index (BMI) of 25-35 kg/m²)
- Age between 18-65 years (inclusive)
- Having blood results for the following tests in the ranges of:
 - HbA1C 20-41 mmol/mol haemoglobin
 - ALT 0-40 IU/L
 - FBC :

| TEST | MALE | FEMALE |
|---------------------------------|-------------|-------------|
| WBC (x10 ⁹ /L) | 4.2-10.6 | 4.2-11.2 |
| RBC (x10 ¹² /L) | 4.23- 5.46 | 3.73-4.96 |

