Statistical analysis perform with IBM SPSS version 23. Graphs prepare with GraphPad Prism version 7.04. Data will be checked for normality using a Shapiro-Wilk test (defined as $P \geq 0.01$). Percentage of weight loss will be calculated using the weight at the end of the intervention divided by the baseline weight multiplied by 100. The results express as mean difference with \pm SEM. Mean of data will be compared within and between groups using a paired t-test or Wilcoxon signed-rank test where applicable. Analysis of variance will assess the impact of two different interventions (IPE and Inulin) on participant blood parameters across the 12-week supplementation period (baseline and week 12), with the supplementation group used to determine between-subjects differences. A p-value ≤ 0.05 will consider significant.

References:

- Abete, I. et al., 2008. Effects of two energy-restricted diets differing in the carbohydrate/protein ratio on weight loss and oxidative changes of obese men. *International journal of food sciences and nutrition*, 60 Suppl 3(783016891), pp.1–13. Available at: <http://www.ncbi.nlm.nih.gov/pubmed/18654910>.
- Bouché, C. et al., 2002. Five-week, low-glycemic index diet decreases total fat mass and improves plasma lipid profile in moderately overweight nondiabetic men. *Diabetes Care*, 25(5), pp.822–828.
- Brown, A.J. et al., 2003. The orphan G protein-coupled receptors GPR41 and GPR43 are activated by propionate and other short chain carboxylic acids. *Journal of Biological Chemistry*, 278(13), pp.11312–11319.
- Chambers, E.S. et al., 2015. A novel dietary strategy to increase colonic propionate production in humans and improve appetite regulation and bodyweight management. *Nutrition Bulletin*, 40(3), pp.227–230. Available at: <http://doi.wiley.com/10.1111/nbu.12157>.
- Chambers, E.S. et al., 2014. Effects of targeted delivery of propionate to the human colon on appetite regulation, body weight maintenance and adiposity in overweight adults. *Gut*, 64(11), pp.1744–1754. Available at: <http://www.ncbi.nlm.nih.gov/pubmed/25500202>.
- Cleave, T.L., 1974. The Saccharine Disease - Chapter 5. In Bristol. Available at: http://journeytoforever.org/farm_library/Cleave/cleave_ch5.html [Accessed February 28, 2016].
- Cordain, L. et al., 2005. Origins and evolution of the Western diet : health implications for the. *The American Journal of Clinical Nutrition*, 81, pp.341–354.

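### Within-arm tests share the p ≤ 0.05 rule with the between-arm comparison, and the plan does not say which supports a conclusion about the propionate ester (IPE)

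*Combined protocol and SAP*

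**What the plan says.** The Statistical Plan covers both kinds of comparison in one sentence: "Mean of data will be compared within and between groups using a paired t-test or Wilcoxon signed-rank test where applicable". With a paired test, the within-group part is naturally read as change from baseline inside each arm. The significance rule is general: "A p-value ≤ 0.05 will consider significant". No primary comparison is named, and the within-group tests are not labelled descriptive.

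The next sentence of that section gives blood parameters a separate analysis: an analysis of variance over baseline and week 12, with supplementation group as the between-subjects factor.

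Both arms diet. Under Visit 2, "a -500 kcal/day diet will be provided to the participants to follow for the rest study period", with no distinction by arm. Under Visit 3, participants take either propionate ester or inulin and are "instructed to mix the contents into their -500 kcal/day individual diet".

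The section supporting the number of volunteers says "we anticipate that a hypo-caloric diet alone will cause a weight loss of 3.0 ± 2.5 kg", and that "the addition of propionate-ester will cause a weight loss of 5.0 ± 2.5 kg". It sizes the trial at 26 per group for a difference between groups.

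**The concern.** The trial asks what IPE adds to a hypocaloric diet. Change from baseline within the IPE arm mixes any supplement effect with the effects of diet and time. The within-arm p-value is validly computed, but it cannot separate these parts. Nor does significance in one arm without significance in the other show that the arms differ.

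The plan gives both kinds of test the same threshold and no order of precedence. For weight, appetite scales, buffet intake, energy expenditure, breath hydrogen, and the urine and stool measures, the only tests named are the paired t-test and the signed-rank test. Neither compares two independent arms. Followed literally, the within-arm tests are the only ones that can be run for those outcomes. At stake is whether a reported significant result on one of them says anything about the supplement.

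**Working it through.** **Inputs from the protocol.** Expected loss is 3.0 kg on diet alone and 5.0 kg with propionate ester, each ± 2.5 kg; n = 26 per group; alpha 0.05; power 0.80; drop-out 25%; 70 recruited.

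**Assumptions.** The 2.5 kg is the SD of the change. Tests are two-sided (the plan does not say). The inulin arm behaves like diet alone.

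**1. The plan's own sample size.** The difference is 5.0 − 3.0 = 2.0 kg, or 2.0/2.5 = 0.8 SD.
- Normal approximation: n = 2 × (1.960 + 0.842)² × (2.5/2.0)² = 24.5, so 25 per group.
- Exact two-sample t: 25.5, so 26, with power 0.807 at 26. A one-sided calculation gives 20, so the stated figure matches a two-sided test.
- Drop-out: 52/(1 − 0.25) = 69.3, so 70.

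The stated figures reproduce, and they belong to a between-arm comparison.

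**2. Within-arm weight test if IPE adds nothing.** Both arms then lose 3.0 ± 2.5 kg.
- Expected t = 3.0/(2.5/√26) = 6.12. An observed t of that size has p of about 2 × 10⁻⁶.
- Power of the paired test at 3.0/2.5 = 1.2 SD and n = 26 is 0.99995. At n = 20 it is 0.9991.
- If the SD of change were 5.0 kg (assumed), power at n = 26 would still be 0.84.
- In 200,000 simulated trials with this common loss, the between-arm t-test was significant in 5.0%.

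**3. One arm significant, the other not, with no IPE effect.** If each within-arm test has power p, the arms are independent and the true change is the same in both, then P(IPE significant, inulin not) = p(1 − p).

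| Within-arm power p | p(1 − p) |
|---|---|
| 0.05 or 0.95 (assumed) | 4.75% |
| 0.30 (assumed) | 21% |
| 0.50 (assumed) | 25% (the maximum) |
| 0.80 (assumed) | 16% |
| 0.99995 (weight, step 2) | about 0.005% |

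Simulation at n = 26 agrees. Assumed shared changes of 0.28, 0.40 and 0.55 SD give the IPE-only pattern in 20%, 25% and 18% of trials. A two-sided between-arm test at 0.05 falsely favours IPE in 0.05/2 = 2.5%.

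**4. Which outcomes have a usable between-arm test.** Glucose, insulin, the gut and appetite hormones and short-chain fatty acids are measured in the Visit 3 blood samples, so the ANOVA covers them. The other outcomes listed under *concern* have only the two paired tests.

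**The case against.** The strongest reply is that the plan does not commit the fallacy. The same sentence also plans a between-group comparison, the sample size is built for one, and blood parameters have an ANOVA by group. A general significance threshold is not a rule for attributing effects to IPE. All of this stands. A reader might infer that the trial relies on within-arm tests alone, or intends to read them as IPE effects. The text says neither; what it lacks is any statement of which comparison carries the conclusion.

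Three further limits also stand.
- A reader might extend the concern to hormones. The ANOVA answers it there.
- The 16% to 25% could be taken as this trial's false-positive rate. It cannot: the documents give no within-arm power for any outcome except weight, the assumed range surrounds the point where p(1 − p) peaks, and the plan contains no such decision rule. For weight the split pattern is practically impossible. The problem there is that the within-arm test is uninformative, not that it creates a false contrast.
- It would be too strong to say that a within-arm result tells us nothing about IPE. The IPE arm's change contains any supplement effect, confounded with diet. Such tests can also legitimately show that weight fell over the study.

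Finally, replacing p-values with per-arm confidence intervals does little by itself, because comparing which interval excludes zero repeats the same error. The fix has to deal with that.

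**Conclusion.** The concern holds as a missing rule about inference with a real consequence, not as a stated misuse. On the plan's own weight figures, a within-arm test at n = 26 is significant with probability about 0.99995 whether or not IPE works. That rests on 2.5 kg being the SD of change and on the inulin arm behaving like diet alone; the protocol's 3.0 kg refers to diet alone, whereas the control arm also takes inulin.

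For outcomes not measured in blood, the gap matters more because no valid between-arm test is named alongside the within-arm ones. How often this would mislead for those outcomes cannot be derived from the documents. The split-significance figures show the mechanism under assumed power and are not estimates for this trial. The change is worth making before analysis. It does not call the sample size or the blood-parameter ANOVA into question.

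**What to change.** Replace the within-group clause in the Statistical Plan with:

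> Any statement that IPE affects an outcome will rest only on the between-arm difference in change from baseline (estimate, 95% CI, and p-value from an independent-groups comparison or baseline-adjusted ANCOVA). Within-arm changes will be reported descriptively (mean, SD, 95% CI), and one arm's result will not be compared with the other's by significance or by whether its CI excludes zero.

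The first sentence does most of the work, and it also supplies the missing between-arm analysis for outcomes not measured in blood. The cost is wording only: no extra participants, visits or data. The small loss is a formal p-value for the overall diet effect, which the within-arm intervals still describe.

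### The between-arm comparison of weight has no baseline adjustment and names paired tests; a prespecified ANCOVA in kg would fit the design, with a precision gain that is unknown and probably small

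*Combined protocol and SAP*

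**What the plan says.** The paragraph on support of number of volunteers (section 2) sizes the trial on weight loss in kg. It expects that "a hypo-caloric diet alone will cause a weight loss of 3.0 ± 2.5 kg" and that "the addition of propionate-ester will cause a weight loss of 5.0 ± 2.5 kg", and concludes that "26 volunteers will be need per group to detect a significant difference between groups" at 0.80 power. It adds that "70 volunteers will be recruited to allow a 25% drop-out rate".

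The Statistical Plan moves to a different scale: "Percentage of weight loss will be calculated using the weight at the end of the intervention divided by the baseline weight multiplied by 100". For the comparison it says: "Mean of data will be compared within and between groups using a paired t-test or Wilcoxon signed-rank test where applicable". The only model in the plan is an analysis of variance, and it is confined to blood parameters. No covariate is named for any outcome.

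Weight is listed explicitly at the screening visit and at the week 4 and week 8 visits. The visit that supplies baseline weight is not named.

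**The concern.** There are three linked problems.

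- **No adjustment.** Baseline weight enters the percentage, the within-group paired comparison and the kg change used for sizing, but it is not a covariate in the between-arm comparison. If it predicts kg lost, the analysis leaves explainable variance in the error term. Randomisation is by sealed envelopes with no stratification stated, so a chance difference in starting weight would also go uncorrected.
- **A percentage is not an adjustment.** Dividing by baseline removes dependence on starting weight only if kg lost is proportional to it. The plan does not argue for that, and Visit 2 sets the same 500 kcal/day deficit for everyone. If kg lost is unrelated to starting weight, the division adds noise.
- **The named tests are paired.** Participants in one arm have no partner in the other, so neither test can make the between-arm comparison.

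At stake is the precision of the propionate-ester minus inulin weight contrast, in a trial planned with little power above 80%.

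**Working it through.** **Inputs from the documents.** Difference 5.0 − 3.0 = 2.0 kg; SD 2.5 kg in each arm (± read as SD); 26 per arm; significance level 0.05, taken as two-sided; dropout 25%.

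**1. The plan's own figure.** A two-sample t calculation with standardised effect 2.0/2.5 = 0.8 gives 25.5 per arm, rounded up to 26. Then 52/0.75 = 69.3, rounded up to 70. Both stated numbers reproduce. A one-sided test would need only 20 per arm, so the two-sided reading is the one that fits.

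**2. Unadjusted power.** SE = 2.5 × √(2/26) = 0.693 kg; noncentrality 2.0/0.693 = 2.88; 50 df; power 80.7%. The comparator is an independent-samples t-test on kg lost, because the paired test named in the plan cannot be applied between arms.

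**3. Power with baseline weight as covariate.** Let r be the correlation of baseline weight with kg lost (**not in the documents**). SE = 2.5 × √(1 − r²) × √(2/26) × √(1 + 1/48), with 49 df. The last factor, 1 + 1/(2n − 4) with n = 26, is the cost of estimating the slope.

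| r | SE (kg) | Power | Change from 80.7% (points) |
|---|---|---|---|
| 0 | 0.701 | 79.9% | −0.8 |
| 0.1 | 0.697 | 80.3% | −0.4 |
| 0.2 | 0.686 | 81.5% | +0.8 |
| 0.3 | 0.668 | 83.5% | +2.8 |
| 0.4 | 0.642 | 86.3% | +5.6 |
| 0.5 | 0.607 | 89.8% | +9.1 |

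Break-even is near r = 0.15.

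**4. Which r is plausible (assumed figures).**

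- Baseline and week 12 weight with equal SD s: r = 2.5/(2s). For s from 8 to 14 kg, r runs from 0.16 down to 0.09, and power is 80.2% to 80.9%, so there is essentially no net gain.
- Loss proportional to weight, mean loss 4 kg, mean weight 80 to 90 kg, SD 10 to 15 kg: r = (4/mean) × SD/2.5, or 0.18 to 0.30. Power is then roughly 81% to 83.5% on the kg scale. The percentage would already capture most of this, so little would be left to gain on that scale.

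**5. Cost of the percentage if kg lost is unrelated to starting weight.** Assume mean weight 85 kg and SD 10 to 15 kg, and let k = (SD/85)². With μ² averaged over the arms as (9 + 25)/2 = 17, the variance of the ratio, put back on the kg scale, is approximately 6.25 × (1 + k) + 17 × k.

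- SD 10: k = 0.0138, variance 6.57, effective SD 2.56, power 78.8%.
- SD 15: k = 0.0311, variance 6.97, effective SD 2.64, power 76.4%.

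Against 80.7%, the loss is about 2 to 4.5 points. Analysing kg lost without a covariate recovers all of it. ANCOVA in kg recovers it less the 0.8-point cost at r = 0.

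**6. Chance imbalance.** One standard error of the baseline difference is √(2/26) = 0.28 baseline SDs. It moves the unadjusted kg contrast by r × 2.5 × 0.277: 0.14 kg at r = 0.2, 0.21 kg at 0.3, 0.35 kg at 0.5, and nothing at r = 0.

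**The case against.** The strongest objection is that the two arguments for adjustment pull against each other. If kg lost does not depend on starting weight, the percentage is inefficient, but r is then 0 and the covariate gains nothing; the remedy is the choice of scale. If loss is proportional to weight, the percentage already does most of the work. Large gains need r of 0.4 or more, and nothing in the documents supports such a value. This stands, and it is why the likely gain is put at nil to a few points.

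It does not remove the case for ANCOVA in kg. That model estimates the slope instead of assuming it, so it performs acceptably in both situations, and it costs at most about 0.8 points if baseline carries no information.

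Three stronger readings might be inferred, and the documents support none of them.

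- **The trial is undersized.** It is not: 26 per arm and 70 in total follow from the stated inputs without adjustment.
- **About nine points of power are being given up.** That needs r = 0.5, which has no source in the plan.
- **The unadjusted contrast is biased.** Under randomisation it is not; chance imbalance is already reflected in its standard error. Adjustment corrects the particular imbalance that occurs.

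It could also be said that the paired-test wording is loose and that an independent-samples test is meant between arms. That may be so, but the sentence names only paired procedures.

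**Conclusion.** The point holds as a low-cost efficiency improvement. The Statistical Plan specifies no baseline adjustment for the between-arm comparison of weight, expresses the outcome as a percentage although the trial was sized in kg, and names tests that do not suit independent arms.

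Moving to ANCOVA in kg changes power from 80.7% to between 79.9% (r = 0) and 83.5% (r = 0.3), with 89.8% only if r reached 0.5. If kg lost is unrelated to starting weight, leaving the percentage scale is worth about 2 to 4.5 points by itself. These figures rest on ± meaning SD, a two-sided test, equal arms of 26 completers and, for the last range, an assumed mean weight of 85 kg with SD 10 to 15 kg. The value of r is unknown. Replacing the paired between-group test is needed whatever r is.

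**What to change.** In the Statistical Plan:

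- Replace the between-group comparison of weight with a prespecified ANCOVA: week 12 weight (kg) as outcome, arm as factor, baseline weight as covariate. With baseline as covariate, using kg change as the outcome gives the same treatment estimate.
- State which pre-supplementation visit supplies baseline weight, and list weight explicitly among the measurements at that visit and at week 12.
- Report the adjusted propionate-ester minus inulin difference in kg with its 95% confidence interval.
- If percentage loss is kept, analyse it in the same model as a supporting result. Correct its formula as well: end weight over baseline weight times 100 is the percentage remaining, and the loss is 100 minus that.
- Keep the paired tests for within-group changes only.

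The cost is a few sentences of plan wording, one degree of freedom and at most about 0.8 points of power. No participants or visits are added, no new type of measurement is needed, and the sample size does not change. The model runs in the SPSS version already named.

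### The ANOVA of blood parameters does not say which term tests IPE against inulin; a week-12 ANCOVA adjusted for baseline should be named

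*Combined protocol and SAP*

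**What the plan says.** The Statistical Plan gives the blood parameters one sentence. It opens "Analysis of variance will assess the impact of two different interventions (IPE and Inulin) on participant blood parameters", gives baseline and week 12 as the two time levels, and ends "with the supplementation group used to determine between-subjects differences". It lists no model terms: no group-by-time interaction, no change score and no baseline covariate.

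The only other rule for comparing means, in the same section, is "Mean of data will be compared within and between groups using a paired t-test or Wilcoxon signed-rank test where applicable". Both tests named there are for paired data, so they supply no contrast between two independent arms. Results are to be given as a mean difference, but the section does not say which difference.

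The visit schedule fixes what baseline means. Of Visit 2 the protocol says "The main objective of this visit is to fully acclimatize the participants to the study before the baseline visit", so Visit 3 (Study visit 1) is the baseline. Participants are randomised at that visit, and blood is drawn "at each time point of 15, 30, 60, 90, 120, 180, and 240 min to measure hormones and metabolites". At Visit 6 (Week 12), "all measurements collected during Study Visit 1 will be repeated".

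**The concern.** With two groups and two visits, a repeated-measures ANOVA yields two terms that involve group, and they answer different questions. The group main effect compares the arms on the average of the two visits. The group-by-time interaction compares the arms on the change between visits. The plan's wording fits either. Its reference to between-subjects differences, read literally, leans towards the main effect, because that is the term usually printed under that label.

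Baseline precedes supplementation, so the arms are expected to be equal there. Averaging the visits therefore dilutes any real effect by half. The interaction does not dilute it, but it is noisier than an analysis that adjusts for baseline.

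The hormones, glucose, insulin and short chain fatty acids are the mechanistic part of the trial. Under one reading a real effect could easily be missed. While the term is left open, it can be chosen once both p-values are known.

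**Working it through.** **The plan's own figure.** Under the heading on the number of volunteers, the protocol assumes losses of 3.0 and 5.0 kg with SD 2.5 kg, a standardised difference of 2.0/2.5 = 0.8, with p = 0.05 and power 0.80. An exact two-sided t calculation gives power 0.791 at 25 per group and 0.807 at 26, so 26 reproduces. With 25% drop-out, 52/0.75 = 69.3, so 70 reproduces. That calculation concerns weight and is not touched by this point. The plan gives no figure for blood parameters.

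**Inputs.** From the documents: two arms, two visits, 26 per arm, significance level 0.05 (two-sided assumed). Not in the documents, so assumed: equal SD of 1 at both visits, correlation r = 0.3, 0.5 or 0.7 between visits, a week-12 difference of d, and Visit 3 blood drawn before the first supplement.

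**What each analysis estimates**

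- Group main effect: effect (0 + d)/2 = d/2; SD of a subject's mean = √((1+r)/2).
- Group-by-time interaction (a t-test on change): effect d; SD = √(2(1−r)).
- ANCOVA of week 12 on baseline: effect d; residual SD = √(1−r²), with one fewer degree of freedom.

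**Sample size for equal power.** The required n is proportional to (SD/effect)², so d cancels from the ratios:

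- main effect to ANCOVA: 2(1+r)/(1−r²) = 2/(1−r)
- interaction to ANCOVA: 2(1−r)/(1−r²) = 2/(1+r)

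| r | main effect / ANCOVA | interaction / ANCOVA |
|---|---|---|
| 0.3 | 2.86 | 1.54 |
| 0.5 | 4.00 | 1.33 |
| 0.7 | 6.67 | 1.18 |

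**Power, as illustration only.** The noncentral t has noncentrality (effect/SD)·√(26/2). For r = 0.5 and d = 0.8:

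- main effect: 0.4/√0.75 = 0.462, times √13 = 1.67, power 0.37
- interaction: 0.8/1 = 0.8, times √13 = 2.88, power 0.81
- ANCOVA: 0.8/√0.75 = 0.924, times √13 = 3.33, power 0.90

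| d (SD units) | r | main effect | interaction | ANCOVA |
|---|---|---|---|---|
| 0.8 | 0.3 | 0.42 | 0.67 | 0.84 |
| 0.8 | 0.5 | 0.37 | 0.81 | 0.90 |
| 0.8 | 0.7 | 0.34 | 0.96 | 0.98 |
| 0.5 | 0.3 | 0.20 | 0.32 | 0.46 |
| 0.5 | 0.5 | 0.18 | 0.42 | 0.53 |
| 0.5 | 0.7 | 0.16 | 0.63 | 0.70 |

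Simulation at d = 0.8 agrees: 0.38/0.81/0.90 at r = 0.5 and 0.35/0.95/0.97 at r = 0.7.

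**Leaving the term open.** The covariance of a subject's mean and change is proportional to var(week 12) − var(baseline). With equal SDs it is zero, so under the null the two tests are independent and the chance that at least one has p ≤ 0.05 is 1 − 0.95² = 0.0975. Simulation (200,000 trials per r) gave 0.097 to 0.098, or 0.095 to 0.097 when the week-12 SD is 1.25 times the baseline SD. Each term alone stayed at 0.049 to 0.051.

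**Several samples per visit.** In a balanced group × visit × sampling-time ANOVA, the group F is the squared t on subject grand means, and the group × visit F is the squared t on subject mean changes. A simulated dataset with seven sampling times confirmed this (6.359 and 19.164 by both routes). The algebra above therefore carries over, with r and d referring to visit means. A simulation of seven times at two visits with d = 0.8 returned mean estimates of 0.40 (main effect), 0.80 (interaction) and 0.80 (ANCOVA).

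**The case against.** Five things can be said for the plan.

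- **The natural reading is the valid one.** Assessing the impact of two interventions over a period with a before and an after suggests group by time, and the between-subjects phrase may only label the group factor. This is fair, and it makes the main-effect figures conditional on the other reading. It does not show which term will be used.
- **ANCOVA is a preference.** The interaction is unbiased over randomisations and holds its type I error. This stands: naming the interaction would be a sufficient repair. ANCOVA is still more efficient at every r considered and costs nothing extra.
- **The sizes rest on assumed inputs.** True of r and of the power table. The halving follows from randomisation alone, and the 9.8% needs no effect size, although it does suppose an analyst who would claim success on either term.
- **There is no single Visit 3 value.** Seven postprandial samples are listed, and the plan does not say how they are summarised. This stands as a related gap. It does not block the ANCOVA, because whichever summary or time point is analysed is measured at both visits.
- **Blood parameters are not the powered outcome.** "A power calculation shows that 26 volunteers will be need per group" refers to weight loss. Agreed, and this limits the weight of the point. These results still carry the trial's mechanistic argument.

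**Conclusion.** The concern holds. The plan does not identify the term that tests IPE against inulin for blood parameters, and no other section settles it. The halved estimate under the main effect needs only randomisation and a baseline taken before supplementation. The sample-size ratios (2.9 to 6.7 for the main effect, 1.54 to 1.18 for the interaction, as r goes from 0.3 to 0.7) also assume equal SDs at the two visits, and they do not depend on effect size. The absolute power values are illustrations. A term fixed in advance would keep type I error near 5%, and if that term were the interaction the only loss would be efficiency. The sponsor should correct this, but it does not threaten the weight-loss comparison or its sample size.

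**What to change.** In the Statistical Plan, state that the treatment effect on each blood parameter is the IPE minus inulin difference at week 12, from an ANCOVA with group as factor and the Visit 3 value of the same parameter as covariate. If the repeated-measures ANOVA is kept, state that the group-by-time interaction, not the group main effect, is the test of treatment.

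In the same place, say which per-visit quantity is analysed (for example an area under the curve over the sampled times, or a named time point), so that this choice is also fixed beforehand.

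The cost is one or two sentences for the test and one more for the per-visit quantity. The data are already collected at both visits, and the software named in the plan can be used unchanged.
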